6.1 General Design

This will be a prospective clinical trial designed to evaluate the incremental benefit of virtual FFR measured from CCTA, compared to invasive FFR and CCTA for the detection of flow-limiting coronary stenosis, as defined by invasive FFR ≤ 0.8 and vessel diameter of $\geq 2\text{mm}$.

572 consecutive patients who present to Lenox Hill Hospital Outpatient Clinics for CCTA due to chest pain or stable angina over a ten month period and meeting the study inclusion criteria are eligible for the study (Figure 1). Our team will employ CCTA-appropriateness criteria to ensure proper selection of patients, derived from the Appropriate Use Criteria for Cardiac Computed Tomography published in 2010 and jointly authored by multiple societies including ACCF, SCCT, and ACR [10]. FFR-CT measurements will be performed by a core laboratory in a blinded fashion. All eligible patients will undergo 64-slice or greater multi detector CCTA and CT-FFR measurements. The severity of the stenosis will be determined on site by level III CCTA readers. Patients with obstructive lesions of (30% to 100% stenosis) will receive Stress-MPI, per SOC protocol, and CT-FFR. Patients with positive Stress-MPI and CCTA (50% - 70%) or positive CCTA (71% to 100%) will undergo ICA with invasive FFR measurement in accordance to accepted guidelines and established practice standard. Those patients with invasively measured FFR ≤ 0.8 and with vessel diameter of $\geq 2\text{mm}$, or those who require revascularizations based on invasively estimated stenosis severity will be considered to have flow-limiting obstructive CAD, while the rest will be considered to have non-flow limiting obstructive CAD (if also $>50\%$ stenosis on ICA). If stenosis severity turns out to be $< 50\%$ after ICA (the gold standard), we will conclude that these patients have non-obstructive CAD. (Figure 1). Patients with 30% to 49% obstructive disease, according to CCTA, will be referred to optimal follow up care only. Any in this group who have positive CT-FFR will return for

ICA with invasive FFR measurement, and follow the protocol for those with 50% to 100% obstruction.

Figure 1:

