In order to assess the primary endpoint of comparison of event rates for patients treated with CCTA and FFR-CT, we will perform a retrospective chart review of Invasive Coronary Angiograms performed at Lenox Hill Hospital from 2014 to 2018. We will specifically review Cardiac Catheterization reports to screen patients and record data for cases where the indication for Catheterization was (1) Positive stress test and/or (2) Positive CCTA. Based on the catheterization report we will determine whether the patient had obstructive coronary artery disease with/without flow limitation, in the same manner and following the same definitions as those used to categorize level of obstruction in subjects enrolled in the prospective cohort of the study. This data will be used as comparison/control group to assess trends and rates of invasive coronary catheterization when no intervention is necessary, in cases where CCTA and/or stress test without CT-FFR was used to determine the need for cardiac catheterization. Only the minimum amount of data required for a robust comparison of event rates will be collected.

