6.2 Primary Study Endpoints

Defining an event as performance of ICA when no intervention is necessary, we expect to compare event rates for patients treated with CCTA and FFR-CT, using t-tests and a multivariate, risk adjusted 90 day hazard model with 95% confidence interval. Our null hypothesis is that outcomes will not vary regardless of which testing is used to assess

obstructive disease. Our alternative hypothesis is that evaluation with FFR-CT as oppose to CCTA will change the event rate. We will also correlate noninvasive and invasive FFR studies.

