8.3 Method for Assigning Subjects to Treatment Groups

This is not a randomized study. Treatment assignments will follow the clinical protocol.

Once the CCTA results are interpreted by the physician, the physician will order CT-FFR exams for patients whose level of stenosis by CCTA standards is 30% to 100%.

If CT-FFR is positive patients will be referred for Cardiac Catheterization and invasive FFR.

If CT-FFR is negative, and level of obstruction is 30 to 49% by CCTA standards, patients will be referred to optimal medical care.

If CT-FFR is negative and level of obstruction is 50% to 70% by CCTA standards, patient will be referred for stress MPI. If stress MPI is positive patients will be referred for Cardiac Cath and invasive FFR. If stress MPI is negative, patients will be referred to optimal medical care.

If the patient has had a stress MPI within one year of the CCTA exam and the CCTA exam result is 50% to 70% obstructive, the physician will rely on the prior stress testing result, rather than repeating the stress test. If the stress testing results was negative, the patient will be referred to optimal medical care. If, in the investigator's opinion, the results indicate that the patient is at increased risk of obstructive disease, when considered with the CCTA findings, the patient will be referred to Cardiac Cath and Invasive FFR.

If CT-FFR is negative and level of obstruction is 70% to 100% by CCTA standard, patient will be referred to Cardiac Cath and Invasive FFR.

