If patient receives a stress MPI, and it is negative, visit 3 will be referral to optimal follow-up care.

If patient receives a stress MPI, and it is positive, visit 3 will be to cardiac cath and invasive FFR.

If patient undergoes a cardiac cath and invasive FFR at visit 2, visit 3 will be a referral to optimal follow-up care.

Visit 4: If patient receives a cardiac cath with invasive FFR at visit 3, visit 4 will be to optimal follow-up care.

10 Risks to Subjects

The risks to subjects in this study are minimal, compared to the risks faced by the population of patients receiving standard of care for potential coronary artery disease and stable chest pain or angina at Lenox Hill Hospital. Most patients will receive the standard of care currently in place, but will have an additional test run (CT-FFR). This test does not require any additional activity of the patient beyond completion of the CCTA with contrast (Standard of Care). This test will be used to assess whether improvements in the standard of care can be made for future patients.

A small percentage of patients, those who have positive CT-FFR, but 30 to 49% obstructive disease by CCTA standard will undergo an additional invasive exam. This exam may identify obstructive disease. If so, the patient will benefit. If not, the patient will undergo an invasive procedure unnecessarily. We believe that very few patients, if any, will fall into this category.

Patients who undergo Invasive FFR and Diagnostic Cardiac Catheterization will face increased risk, as compared to standard of care. According to the NIH National Heart Lung and Blood Institute, this procedure is very common, and rarely causes serious problems. [22] However, complications can include bleeding, infection and pain at the catheter insertion site. On rare occasions the catheter can scrape or poke a hole in a blood vessel during insertion

causing damage to the blood vessel. Patients may also experience an allergic reaction to the dye that is used during the procedure. Less common reactions include arrhythmias, or irregular heart beats; kidney damage caused by the dye that is used during the procedure; blood clots that can trigger stroke or heart attack or other serious problems; low blood pressure; or a buildup of fluid in the sac that surrounds the heart. This may cause the heart not to beat properly. [22]

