14.2 Statistical Methods

Statistical Aims

1. *To determine the sensitivity, specificity, positive predictive value (PPV) and negative predictive value (NPV) of the CCTA test (with or without stress MPI, as specified in Figure 1) + CT-FFR evaluation to identify chest pain patients with flow-limiting obstructive CAD. The ICA test will be used as gold standard.*
2. *To determine inter-observer reliability of CCTA and CCTA+CT-FFR test readings between an experienced and a non-experienced reader, and compare the results between CCTA and CCTA+CT-FFR; to determine the intra-observer reliability of CCTA and CCTA-FFR reading, for both the experienced and non-experienced reader, and for each reader compare the results between CCTA and CCTA+CT-FFR.*

3. To identify factors of return visit within 90 days in patients who had no ICA test or a negative ICA test result.

Outcome Variables

- *CCTA+CT-FFR test status (Positive/Negative). The test is deemed positive if ICA is required and negative if ICA is not required (see Figure 1).*
- *ICA (gold standard) test status (Positive / Negative). ICA is deemed positive if $FFR < 0.8$ and vessel diameter $>= 2\text{mm}$ or if the patient requires revascularizations based on invasively estimated stenosis severity. It is deemed negative otherwise.*
- *Return visit within 90 days (Y/N). Return visit is defined as patients who return for unplanned cardiac care, including emergency room visits, emergency hospital admissions, urgent percutaneous coronary intervention, coronary artery bypass graft, or acute myocardial infarction. Descriptive statistics (n, mean, median, standard deviation, IQR, frequencies and percentages) will be used to describe the demographic and clinical characteristics of the whole sample.*

For Aim 1, sensitivity, specificity, PPV, and NPV will be computed using the ICA result as the ‘true’ flow-limiting obstructive CAD status and the CCTA+CT-FFR test result as the ‘test’ status. Exact binomial 95% confidence intervals will be computed.

For Aim 2, inter- and intra-observer reliability for the CCTA and CCTA+CT-FFR tests will be assessed using Cohen’s Kappa coefficient. Dependent Kappa coefficients will be compared using a method developed by Donner et al .

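### Control catheterizations need not have had invasive FFR, yet an unmeasured, unrevascularized control lesion counts as a negative ICA by default, so the primary comparison partly reflects how often FFR was measured

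*Combined protocol and SAP*

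**What the plan says.** **Primary event.** Section 6.2 sets it out as follows: "Defining an event as performance of ICA when no intervention is necessary". Rates are to be compared between cohorts "using t-tests and a multivariate, risk adjusted 90 day hazard model with 95% confidence interval".

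**Prospective cohort.** Under section 6.1, patients with a qualifying CCTA or stress result "will undergo ICA with invasive FFR measurement in accordance to accepted guidelines and established practice standard". Section 8.3 couples the two procedures in the same way: "If CT-FFR is positive patients will be referred for Cardiac Catheterization and invasive FFR". Section 9 repeats this.

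**Controls.** Sections 6.1, 7.4 and 9 describe a chart review of ICAs from 2014 to 2018, selected because the indication was a positive stress test and/or a positive CCTA. Presence or absence of flow limitation is then read from the catheterization report, "in the same manner and following the same definitions as those used to categorize level of obstruction in subjects enrolled in the prospective cohort". Section 6.1 says that these data supply the comparison rate for the primary endpoint. It also limits collection to the minimum needed.

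**Classification rule.** In section 14.2 an ICA is positive if FFR is below the cut-off in a vessel of at least 2 mm, or if revascularization is required on invasively estimated severity. For everything else: "It is deemed negative otherwise". Section 6.1 has the same default: patients not meeting the flow-limiting definition are taken as non-flow-limiting (over 50% stenosis on ICA) or non-obstructive (under 50%). Neither section has a category for FFR not measured.

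**The concern.** The same definition is applied to two cohorts that may hold different information. Where FFR is missing, the FFR limb of the rule cannot be met, and the lesion can be positive only through revascularization. If it was not revascularized, the rule calls it negative. That is a missing value recorded as a finding. If FFR was measured less often in the controls, the control negative rate is pushed up, which makes CT-FFR look better.

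A second mechanism runs the other way. With no FFR value, an operator may revascularize on visual severity, and the control is positive. With a reassuring FFR value, the operator may leave the same lesion alone, and the prospective patient is negative. This lowers the control negative rate relative to the prospective one.

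At stake is the interpretation of the primary comparison. A difference between cohorts, or its absence, could partly reflect how often invasive FFR was done. More controls would not help, because this is bias and not sampling error. The risk-adjusted model cannot correct it while FFR status goes unrecorded.

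**Working it through.** **1. The plan's own figure (section 14.1).** Inputs: 14% reduced to 6%, two-sided one-sample chi-square test, alpha 0.05, 80% power.

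n = [1.960 × √(0.14 × 0.86) + 0.842 × √(0.06 × 0.94)]² / 0.08² = 120.99, so 121 ICAs.

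Total completing: 121 / (0.60 × 0.35) = 576.2, which agrees with 576.

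Both figures reproduce. The calculation treats 14% as a fixed, known rate, so it has no term for how control status is ascertained. The planned difference is 14 − 6 = 8 points.

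**2. The overstatement from the default rule.** Let c be the observed control negative rate, s the share of control ICAs that are unmeasured and unrevascularized, and q the share of those that FFR would have called positive.

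Overstatement = s × q, with s ≤ c.

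The constraint holds because every such ICA is counted as negative, so s is part of c.

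**3. Illustration.** The documents give neither s nor q, and no observed rate for these controls. Assume c = 14% (the section 14.1 figure, which comes from other data) and q = 20% to 50%.

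| s | q = 20% | q = 35% | q = 50% |
|---|---|---|---|
| 0% (every unrevascularized control measured) | 0 | 0 | 0 |
| 7% | 1.4 points | 2.5 points | 3.5 points |
| 14% (the maximum) | 2.8 points | 4.9 points | 7.0 points |

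The range is 0 to 7 points against a planned 8. The ceiling is c × q, so it moves in proportion if the actual control rate is not 14%.

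**4. What this does to a test of two cohorts.** Assume 121 prospective and 500 control ICAs (the control number is not in the documents), a pooled two-proportion z-test, and no CT-FFR effect. The true rate in both cohorts is then 14% less the overstatement.

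- Overstatement 0 (14.0% against 14.0%): rejects 5% of the time.
- Overstatement 2.8 points (11.2% against an observed 14.0%): 11%.
- Overstatement 4.9 points (9.1% against 14.0%): 28%.
- Overstatement 7.0 points (7.0% against 14.0%): 56%.

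For the last line, the pooled rate is (121 × 0.07 + 500 × 0.14) / 621 = 0.1264. The null SE is 0.0337 and the alternative SE is 0.0279. Then (0.07 − 1.960 × 0.0337) / 0.0279 ≈ 0.14, which gives a probability of about 0.56.

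**5. The opposite direction.** Suppose the true rates are 14% and 6%, and visual revascularization lowers the observed control rate. With the same sample sizes, power is 71% with no shift, 41% if the control rate falls by 2.5 points to 11.5%, and 16% if it falls by 5 points to 9%. These shifts are also assumptions.

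**6. Net effect.** Let u be the share of control ICAs without FFR. Among those, let m be the share that FFR would make positive but the default calls negative, and r the share that FFR would make negative but that count as positive after visual revascularization. The net bias is u × (m − r). It is zero only if every control was measured or the two errors cancel. The documents fix none of the three.

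**The case against.** **Invasive FFR was accepted practice at this hospital.** Sections 6.1 and 9 say so, and the controls come from the same hospital. This stands in part: many controls may have been measured, and the bias may be small. But the plan neither requires nor records FFR in controls, so it could not show this.

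**Section 10 does not show that FFR was unusual.** A reader might infer that it does, from "Patients who undergo Invasive FFR and Diagnostic Cardiac Catheterization will face increased risk, as compared to standard of care". That sentence concerns FFR and catheterization together, and follows a paragraph on patients who have an additional invasive exam. The complications listed are those of catheterization. Sections 12, 15.5 and 15.7.1 likewise place the added risk in an extra catheterization. The sentence is not evidence either way on FFR in controls.

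**The default rule belongs to Aim 1, not to the primary event.** The rule does sit under the outcome variables of section 14.2, and section 6.2 words the event in terms of intervention. But section 6.1 obtains the control rate by classifying flow limitation under the same definitions and has its own default. Section 14.2 gives no separate operational definition of the event.

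**The revascularization limb applies to both cohorts.** This stands. A prospective lesion judged to need revascularization on estimated severity is positive whatever its FFR. The opposing error therefore arises only when an FFR result changes the decision to revascularize.

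**A PCI/CABG event would remove the problem.** A reader might infer this, because intervention is visible in both cohorts. It would not: if FFR results influence who is revascularized, the event still depends on how often FFR was measured. Restricting to measured ICAs is not clean either, since it selects on the operator's choice to measure.

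**Conclusion.** The point holds as a gap in the plan: the default rule turns missing FFR into a negative result in the comparator for the primary endpoint, and nothing to be collected would reveal how often. On the assumptions stated (observed control rate 14%, 20-50% of unmeasured lesions FFR-positive), the default overstates the control negative rate by 0 to 7 points, against a planned 8.

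Three stronger readings are not supported. A reader might enter larger shares, for example 30% × 50% = 15 points. That cannot coexist with an observed 14%, because the unmeasured, unrevascularized ICAs are a subset of the negatives. A reader might conclude that the bias favours CT-FFR, but the effect of FFR on revascularization decisions works against it and the net direction is unknown. A reader might also conclude that most controls went unmeasured, and the documents do not say so.

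This should be fixed. The default creates a risk of misclassification that the plan cannot assess, but neither its presence in these controls nor its size is established.

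**What to change.** In sections 6.1 and 14.2:

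- From every control and prospective ICA report, extract whether FFR was measured (Y/N), the FFR value, the angiographic stenosis, and whether PCI or CABG was performed or recommended.
- Code an ICA with an unrevascularized lesion of 50% or more and no FFR value as indeterminate in both cohorts, instead of negative.
- Report the primary comparison with bounds: all indeterminates negative, then all positive. Report the share with FFR measured in each cohort beside it.
- Add two sensitivity analyses: ICAs with FFR measured in both cohorts, and the event of no PCI or CABG performed or recommended. State that the first selects on the choice to measure and that the second is still influenced by FFR use, so neither fully removes the measurement effect.
- Reconcile the FFR cut-off while editing: section 6.1 includes a value of exactly 0.8 as positive and section 14.2 does not.

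The cost is a few extra fields on the chart-review form and some SAP wording. The result also becomes a range instead of one number, and the range will be wide if many ICAs are indeterminate.

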7.1 Inclusion Criteria

1. Patients must be capable of giving informed consent.
2. Patients must be able to cooperate with technician performing the procedure.
3. Patients must have BMI <= 50.
4. Patients must have non-STEMI EKG without acute changes

5. *Patients must present to Lenox Hill Ambulatory CCTA Clinic with medically necessary appointment for CCTA for the purpose of evaluation coronary stenosis for the provisional diagnoses of chest pain or angina or angina equivalent.*
6. *Patient must be able to take nitroglycerin and beta blockers.*

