7.4 Subject Recruitment and Screening

Patients scheduled to present or presenting to the Lenox Hill Ambulatory Care CCTA Clinic for evaluation of coronary stenosis with the provisional diagnosis of chest pain or angina will be offered the opportunity to participate in this clinical trial. If possible, patients will be contacted in advance of the visit by the study coordinator and educated on the study. All eligible patients will receive education about the study and offered the opportunity to participate upon arrival to the clinic.

The study coordinator, cardiology fellow, or cardiologist will take the patient's medical history as it relates coronary stenting, CABG and other cardiac risk factors (including smoking, family history of heart disease, hyperlipidemia, diabetes, hypertension.) Routine preparation for CCTA will be conducted by clinic staff. As part of this activity patient height and weight will be obtained, and a blood draw for Serum Creatinine to calculate patient eGFR will be taken.

In order to assess the primary endpoint of comparison of event rates for patients treated with CCTA and FFR-CT, we will perform a retrospective chart review of Invasive Coronary Angiograms performed at Lenox Hill Hospital from 2014 to 2018. We will specifically review Cardiac Catheterization reports to screen patients and record data for cases where the indication for Catheterization was (1) Positive stress test and/or (2) Positive CCTA. Based on the catheterization report we will determine whether the patient had obstructive coronary artery disease with/without flow limitation, in the same manner and following the same definitions as those used to categorize level of obstruction in subjects enrolled in the prospective cohort of the study.

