14.1 Sample Size Determination

Based on data from Stony Brook and confidential data HeartFlow reported from providers who have been using CT-FFR in a similar manner as we propose for this study, we estimated that about 60% of stable chest pain patients who had CCTA were diagnosed with coronary stenosis of 30% to 90% and received CT-FFR. Of these patients, about 35% had an ICA test, and 14% of those had a negative ICA test result (i.e. the false-positive rate of CCTA+CT-FFR was 14%). A sample of 121 patients who received ICA will yield 80% statistical power of detecting a 60% reduction in the false-positive rate (from 14% to 6%), based on a two-sided one sample Chi-square test with 0.05 significance level. Assuming a similar prevalence of flow-limiting obstructive CAD and assuming that similar proportions of stable chest pain patients who had CCTA will receive CCT-FFR and then ICA, 576 stable chest pain patients who had CCTA need to be complete the clinical trial. In order to target 576 subjects completing the trial, we estimate that number of patients, it will be necessary to 594, because 18 patients who enrolled were screen failures.

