For Aim 3, a survival analysis regression model will be carried out to determine which risk factors are associated with “time-to-return visit”. Proposed factors will include age, sex, race, diabetes, hyperlipidemia, hypertension, active smoking and smoking history, family history of premature heart disease, obesity, and the number of cardiac risk factors present. In addition we will consider adding whether the admission was surgical or medical, and the MS or AP DRG case weight as a measure of severity.

Statistical Methods

Descriptive statistics (n, mean, median, standard deviation, IQR, frequencies and percentages) will be used to describe the demographic and clinical characteristics of the whole sample.

For Aim 1, sensitivity, specificity, PPV, and NPV will be computed using the ICA result as the ‘true’ flow-limiting obstructive CAD status and the CCTA+CT-FFR test result as the ‘test’ status. Exact binomial 95% confidence intervals will be computed.

For Aim 2, inter- and intra-observer reliability for the CCTA and CCTA+CT-FFR tests will be assessed using Cohen’s Kappa coefficient. Dependent Kappa coefficients will be compared using a method developed by Donner et al .

For Aim 3, a survival analysis regression model will be carried out to determine which risk factors are associated with “time-to-return visit”. Proposed factors will include age, sex, race, diabetes, hyperlipidemia, hypertension, active smoking and smoking history, family

history of premature heart disease, obesity, and the number of cardiac risk factors present. In addition we will consider adding whether the admission was surgical or medical, and the MS or AP DRG case weight as a measure of severity.

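### Aim 3 lists obesity with no coding; continuous BMI from the measured height and weight would avoid a likely loss of information at no cost

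*Combined protocol and SAP*

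**What the plan says.** Aim 3 in section 14.2 is "To identify factors of return visit within 90 days in patients who had no ICA test or a negative ICA test result". The method is given as follows: "a survival analysis regression model will be carried out to determine which risk factors are associated with" time to return visit. The factor list opens with "Proposed factors will include age, sex, race, diabetes, hyperlipidemia, hypertension, active smoking and smoking history" and ends with "history of premature heart disease, obesity, and the number of cardiac risk factors present". Two more candidates are possible: "In addition we will consider adding whether the admission was surgical or medical, and the MS or AP DRG case weight".

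The word obesity stands without a cut-off, a category definition or a stated yes/no form. BMI is not in the list.

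Elsewhere the plan shows that the underlying measurement exists. Section 7.4, on routine preparation for the scan, says "As part of this activity patient height and weight will be obtained". Section 7.1 requires "Patients must have BMI <= 50", and section 7.2 repeats the limit as an exclusion. The cardiac history items named in section 7.4 are smoking, family history, hyperlipidemia, diabetes and hypertension. Obesity is not among them, although that list is not presented as complete.

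**The concern.** Obesity is the name of a category. In section 14.2 it sits among diagnoses that are present or absent and next to a count of risk factors, so an analyst would most likely code it yes/no. The natural source for it is the measured height and weight, which means cutting a measured quantity in two. Such a cut treats patients just either side of it as different and all patients on one side as alike.

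Aim 3 exists to find factors associated with return visits, so what is at stake is the chance of detecting a BMI effect if there is one. A linear BMI term uses one degree of freedom, the same as a yes/no term, so keeping the full measurement does not enlarge the model. With no cut-off fixed in advance, it could also be chosen after the data are seen.

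**Working it through.** **1. The plan's own figures.** Section 14.1 has the only sample-size calculation. It gives no figure for Aim 3, but it does allow the Aim 3 set to be sized. Inputs: 14% against 6%, 80% power, "two-sided one sample Chi-square test with 0.05 significance level".

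- n = [1.960 × √(0.14 × 0.86) + 0.842 × √(0.06 × 0.94)]² / (0.14 − 0.06)² = 120.99, so 121, as stated.
- Completers: 121 / (0.60 × 0.35) = 576.2, against the stated 576. Both figures reproduce.

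**2. Size of the Aim 3 set.** Patients with a positive ICA are left out. Expected ICAs: 576 × 0.21 = 120.96.

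- With 14% negative: 576 − 0.86 × 120.96 = 472.
- With 6% negative: 576 − 0.94 × 120.96 = 462.

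The documents state no return-visit rate. Assumed rates of 1%, 5% and 15% give about 5, 23–24 and 69–71 events. The list has at least 11 terms (age, sex, race, diabetes, hyperlipidemia, hypertension, active smoking, smoking history, family history, obesity, risk-factor count). That is about 0.4, 2.1 and 6.4 events per term, and fewer if the two optional terms are added.

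**3. Information kept by a yes/no split.** Assume that BMI is normal, that its effect on the log hazard is linear, and that a share p of patients lies above the cut c. The share of information kept is φ(c)² / [p(1 − p)], where φ is the standard normal density. For p = 0.35, c = 0.385 and φ(c) = 0.370, so 0.370² / (0.35 × 0.65) is about 0.60.

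| Share obese (assumed) | Kept | Lost |
|---|---|---|
| 20% | 49.0% | 51.0% |
| 25% | 53.9% | 46.1% |
| 30% | 57.6% | 42.4% |
| 35% | 60.3% | 39.7% |
| 40% | 62.2% | 37.8% |
| 50% | 63.7% | 36.3% |

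At 35% the split needs 1/0.603 = 1.66 times as many events for the same power. This relative loss does not depend on the number of events.

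**4. Sensitivity to the shape of BMI.** Simulated normal and lognormal BMI (assumed means 27–30, SD 5–7, limited to 50, cut at 30) put about 25% to 51% of patients above the cut and gave losses of 34% to 43%. Moderate skewness therefore does not change the picture.

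**5. Sensitivity to the shape of the effect.** If risk changes only in a step at the cut, the yes/no form loses nothing, and a linear BMI term could do worse.

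**6. Single-covariate illustration only.** Power = Φ(√(events × share kept) × ln HR − 1.96), with an assumed hazard ratio of 1.5 per SD and 35% obese. At 24 events it is 51% for continuous BMI and 34% for the split. At 5 events it is 15% and 11%. These figures ignore every other term, so they do not describe the planned model.

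**The case against.** A reader might infer that the plan enters obesity as yes/no and so throws away about 40% of the BMI information. The documents do not support that as a statement of fact. Section 14.2 gives only a bare label in a list of proposed factors, and age, race and smoking have no stated coding either. What can be shown is that the coding is unspecified and that yes/no is the natural reading. The 40% needs a near-normal BMI, roughly 30% to 40% of patients above the cut and a linear effect, none of which is in the documents.

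A reader might also take a power comparison as showing what Aim 3 stands to lose. It does not. No event rate is given, the hazard ratio is assumed, and the model has at least 11 terms. At the lower assumed event counts either coding would have little power, and the coding of one covariate is not what limits Aim 3.

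It is also fair to say that clinical obesity is easy to interpret, and that the overlap between the risk-factor count and its own components is the weightier problem in the same sentence. If the count is the sum of the listed yes/no factors, it is exactly collinear with them.

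These objections narrow the point without removing it. Continuous BMI should be available without new data, uses no extra degree of freedom, and is the better default unless there is reason to expect a step at a particular cut. The documents offer no such reason.

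**Conclusion.** The point holds as a small improvement to a non-primary model. The plan names obesity for Aim 3 and leaves its coding open, although the measurements needed for continuous BMI are obtained. If the yes/no reading is what is meant, and BMI is roughly normal with a linear log-hazard effect, the loss for that one covariate is about 36% to 51% as obesity prevalence runs from 50% down to 20%. Under a true threshold at the cut the loss is zero.

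The primary comparison, Aims 1 and 2 and the sample size are untouched. It would be wrong to read the point as explaining, or curing, the shortage of events per term that is likely in this model.

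**What to change.** In section 14.2, Aim 3, replace obesity with BMI as a continuous covariate, calculated from the measured height and weight, and say that it enters as a single linear term. Keep obesity as a category for the descriptive tables, with its cut-off stated. The Aim 3 paragraph is printed twice in section 14.2, so both copies need the edit.

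If obesity also contributes to the risk-factor count, say so. The yes/no status would then still reach the model through the count. That overlap, and the number of terms, need their own solution.

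The cost is SAP wording only: no new data, no extra degree of freedom and no effect on the sample size.
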